7.3.5.1. Blood pressure/body weight

Blood pressure systolic, blood pressure diastolic, and body weight

7.3.5.2. Cardiac function test

Left ventricular ejection fraction (LVEF), left ventricular end-diastolic dimension (LVDd), and left atrial diameter (LAD) confirmed by echocardiography

7.3.5.3. Clinical laboratory tests

Serum creatinine, serum potassium, BUN, plasma BNP, and serum NT-proBNP

7.3.6. Clinical evaluation

Enter the evaluation result obtained by using the following evaluation scale for clinical evaluation.

7.3.6.1. NYHA Functional Classification

For clinical evaluation, enter whether or not evaluation based on NYHA Functional Classification is done and the evaluation result. The evaluation result to be entered should be the one obtained on the last day of the observation period. If treatment with this drug is discontinued, enter the result of evaluation implemented on the last day of observation. However, if no evaluation is done in the relevant period, enter the evaluation result obtained in the period closest to the relevant period.

- (1) Whether or not evaluation based on the NYHA Functional Classification is done
- (2) Date of evaluation based on the NYHA Functional Classification

(3) Results of evaluation based on the NYHA Functional Classification

Reference) NYHA Functional Classification

- Class I: Having a heart disease, but with no limitation of physical activity. Ordinary physical activity does not cause marked fatigue, palpitations, dyspnoea, or anginal pain.
- Class II: Having a mild limitation of physical activity. No symptom at rest. Ordinary physical activity causes fatigue, palpitations, dyspnoea, or anginal pain.
- Class III: Having a severe limitation of physical activity. No symptom at rest. Exertion less than ordinary activity causes fatigue, palpitations, dyspnoea, or anginal pain.
- Class IV: Any physical activity is limited due to a heart disease. A symptom of heart failure or anginal pain is present even at rest. These symptoms can be exacerbated by slight exertion.

(Source: Igaku Shoin's Medical Dictionary 2nd Edition, issued on February 15, 2009)

7.3.6.2. Clinical effectiveness (investigator's evaluation)

The investigator will evaluate this drug based on the following items for judging the clinical effectiveness on the last day of the observation period as compared to the status before the administration of this drug (including the start date of administration), and enter the evaluation date and its results. If treatment with this drug is discontinued, enter the result of evaluation implemented on the last day of observation. However, if there is no result for the relevant period, enter the result obtained in the period closest to the relevant period.

Clinical effectiveness

- (1) Yes
- (2) No
- (3) Unavailable (In this case, the reason should be recorded.)

7.3.7. Presence/absence of pregnancy (in women only)

Enter the presence/absence of pregnancy between the start date of administration and the last day of the observation period.

7.3.8. Adverse events

Regardless of causal relationship with this drug, the following information related to all adverse events that occur between the start of administration and the last day of the observation period (the last day of observation if treatment is discontinued) should be entered in the section of adverse events. Conduct a detailed investigation separately if the sponsor judges it necessary.

- · Presence/absence of adverse event
- Name of adverse event
- Category of adverse event
 Also enter whether the entered adverse event is an "even
 - Also enter whether the entered adverse event is an "event related to hypotension" or an "event related to hyperkalaemia."
- Date of occurrence
- · Procedure ([1] Change of treatment with this drug; [2] Additional treatment for the adverse event)
- Seriousness
- Whether or not the event(s) has led to death; Whether or not the event(s) has led to hospitalization. If the event has led to death, enter information on whether or not it is "cardiovascular death," or if the event has led to hospitalization, enter information on whether or not it is "hospitalization due to a cardiovascular event."
- Outcome of the adverse event to present; Outcome date

Causal relationship with this drug

If there is any adverse event related to abnormal changes in test values from clinical laboratory tests and physiological function tests, etc., enter the following information in the section of tests related to adverse events.

- · Laboratory parameter
- · Site reference value
- Unit
- Test date
- Results

Cardiovascular deaths are defined as deaths due to any of the following causes:

- Cardiac failure
- Myocardial infarction
- Arrhythmia (Atrial fibrillation, Atrial flutter, Arrhythmia supraventricular, or Ventricular arrhythmia)
- Stroke or cerebrovascular attack
- Other causes related to cardiovascular system

If any adverse event corresponding to "renal impairment" is observed, enter information on drugs other than this drug and "7.3.4.1.1. Relevant drugs" (Refer to the section "7.3.4.2. Other previous treatment drugs and concomitant drugs [collect information for subjects who have any adverse event corresponding to "renal impairment"]).

Note: Adverse events are any and all unfavorable events (including clinically significant abnormal changes in laboratory tests) occurring in patients after starting treatment with this drug regardless of their causal relationship. Serious adverse events are any unfavorable medical occurrences that result in death, are life-threatening, require (or prolong) hospitalization, cause persistent or significant disability/incapacity, result in congenital anomalies or birth defects, or are other conditions which represent significant health hazards.

7.3.9. Survival confirmation

Regarding the status from the start of administration to Week 52, enter the following information in the section of survival confirmation.

- Last date of survival confirmation
- · Result of survival confirmation

7.3.10. Major investigation items

7.3.10.1. Hyperkalaemia

Due to the mechanisms of action of this drug, a risk of hyperkalaemia is expected. It was observed as an adverse reaction in clinical studies by the time of approval. It is also known as a clinically-significant adverse reaction to similar drugs, and may become severe at the time of onset, thereby possibly threatening the life, and as such, it is specified as an important identified risk. For this event specified as a major investigation item, information on the onset date of the adverse event, procedure (change of treatment with this drug; additional treatment for the adverse event), seriousness, outcome, causal relationship with this drug, and factors for the adverse event other than this drug will be collected, and risk factors and onset time will be investigated.

7.3.10.2. Events related to hypotension

Due to the mechanisms of action of this drug, the possibility that adverse events related to hypotension may occur cannot be ruled out, and associated secondary events (fall, loss of consciousness, etc.) may occur, possibly leading to clinically-significant events, and therefore these events are specified as important identified risks. For this event specified as a major investigation item, information on the onset date of the adverse event, procedure (change of treatment with this drug; additional treatment for

the adverse event), seriousness, outcome, causal relationship with this drug, and factors for the adverse event other than this drug will be collected, and risk factors and onset time will be investigated.

7.4. Data sources

In this study, the investigators extract the necessary information from source documents such as medical records in accordance with the protocol.

7.5. Sample size

7.5.1. Planned sample size

A total of 1000 CHF patients as subjects included in the safety analysis set (including at least 300 patients with moderate renal impairment)

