7.2.4. Planned study period

The planned period covered by this study is as follows.

Investigation period: July 2017 to June 2020

Registration period: July 2017 to June 2018

(Even before the end of the registration period, the registration will be terminated if the target number of subjects is reached.)

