7.5.2. Rationale for sample size

Table 5 shows the number and proportion of cases of adverse events related to hyperkalaemia and renal impairment that occurred within 52 weeks (364 days) after the start of administration, for which a causal relationship could not be ruled out, in all CHF patients and patients with moderate renal impairment in the domestic Phase III study (Study A6141114) and the foreign Phase III study (Study EMPHASIS-HF).

Table 5. Adverse Events related to Hyperkalaemia and Renal Impairment that Occurred within 52 Weeks (364 Days) after the Start of Administration in Eplerenone Group for which Causal Relationship Could Not Be Ruled Out - Safety Analysis Set

Patients with moderate renal impairment eGFR < 50 mL/min/1.73m ²	All CHF patients
N=37	N=111
2 (5.4)	3 (2.7)
0	1 (0.9)
1 (2.7)	1 (0.9)
N=224 a	N=1360
20 (8.9)	56 (4.1)
1 (0.4)	4 (0.3)
6 (2.7)	12 (0.9)
	impairment eGFR < 50 mL/min/1.73m ² N=37 2 (5.4) 0 1 (2.7) N=224 a 20 (8.9) 1 (0.4)

n (%)

In Study A6141114, the ratio of patients with moderate renal impairment to all CHF patients in Japanese was 34.4% (76/221). Taking into account this result and the results of a Japanese epidemiological survey³), the ratio of patients with moderate renal impairment to CHF patients in Japan is estimated to be approximately 30%. Given that the target sample size of all CHF patients is 1000 patients, the number of patients with moderate renal impairment is expected to be approximately 300-350.

As shown in Table 5, the incidence rate of adverse events related to renal impairment for which a causal relationship could not be ruled out was 3.1% (8/261) in patients with moderate renal impairment in the combined results from Study A6141114 and Study EMPHASIS-HF conducted in CHF patients with systolic dysfunction in which the same primary endpoint (cardiovascular deaths or hospitalization due to heart failure) was compared to a placebo treatment group. Assuming that 3.1% is the true incidence rate of adverse events related to renal impairment for which a causal relationship cannot be ruled out in patients with moderate renal impairment, the expected number of cases of adverse events related to

^a: Including two patients with eGFR <30 mL/min/1.73m².

renal impairment for which a causal relationship cannot be ruled out is 9.3-10.9 when collecting 300-350 patients with moderate renal impairment.

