Also, assuming that 8.4% (22/261) is the true incidence rate of adverse events related to hyperkalaemia for which a causal relationship cannot be ruled out in patients with moderate renal impairment, similarly to the above-mentioned method, the expected number of cases of adverse events related to hyperkalaemia for which a causal relationship cannot be ruled out is 25.2-29.4.

If events which true incidence rate is 3.1% and 8.4% are observed in 300 patients, the estimated incidence rate will be 1.1%-5.1% and 5.3%-11.5%, respectively, with a probability of approximately 95%.

Assuming that the true incidence rate of adverse events related to renal impairment and hyperkalaemia in all CHF patients for which a causal relationship cannot be ruled out is 1.2% (18/1471) and 4.0% (59/1471), respectively, the expected number of cases of adverse events for which a causal relationship cannot be ruled out is 12.0 and 40.0, respectively, when collecting 1000 CHF patients. Events can be observed in approximately 6-19 patients and 28-53 patients, respectively, with a probability of approximately 95%.

If events which true incidence rate is 1.2% and 4.0% are observed in 1000 patients, the estimated incidence rate will be 0.5%-1.9% and 2.8%-5.2%, respectively, with a probability of approximately 95%.

As described above, regarding adverse events related to hyperkalaemia and renal impairment for which a causal relationship cannot be ruled out, a target sample size of 1000 patients may enable evaluation of the safety profile between clinical studies and use-results surveys in terms of patient background including the presence/absence of comorbid moderate renal impairment as well as seriousness, outcome, etc. of adverse events.

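### Protocol 7.5.1 states 300 patients with moderate renal impairment as a minimum, but 7.5.2 supports 300 only as the count expected at a 30% share of 1000

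*Protocol*

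**What the plan says.** Section 7.5.1 sets the planned size: "A total of 1000 CHF patients as subjects included in the safety analysis set", "including at least 300 patients with moderate renal impairment".

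Section 7.5.2 explains where the 300 comes from. It cites the domestic Phase III study, where 76 of 221 patients (34.4%) had moderate renal impairment, and a Japanese epidemiological survey. From these it concludes that "the ratio of patients with moderate renal impairment to CHF patients in Japan is estimated to be approximately 30" per cent. With 1000 patients in all, "the number of patients with moderate renal impairment is expected to be approximately 300-350". The subgroup precision is then given at a single size: "If events which true incidence rate is 3.1% and 8.4% are observed in 300 patients", the 95% ranges are 1.1%-5.1% and 5.3%-11.5%.

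On closing registration, section 7.2.4 gives a period of July 2017 to June 2018 and adds that, before then, "the registration will be terminated if the target number of subjects is reached". Section 7.2.5 also refers to a target number of patients. Neither mentions the renal subgroup. The section on reporting milestones to the PMDA (section 14) asks for the number and ratio of patients with moderate renal impairment when registration is complete.

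**The concern.** A minimum and an expectation are different promises. Section 7.5.1 words 300 as a floor, while 7.5.2 derives it as the mean count at the planning share. A floor set at the mean is missed about half the time unless something in the conduct of the study enforces it, such as a quota, a continuation rule or a margin in the total. The protocol describes none of these, and the only stated report of the subgroup count comes when registration has ended.

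The subgroup matters because it is the population of the primary objective (Protocol 6.2, SAP 2.2). Its precision is quoted only at 300, so a reader would take those ranges as the worst case. They are the ranges at the expected count.

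**Working it through.** **Inputs.** Total 1000 and minimum 300 (7.5.1); share about 30%, domestic share 76/221, expected count 300-350, event rates 3.1% and 8.4% (7.5.2).

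**Step 1: reproduce the plan's figures.**
- Expected count: 1000 × 0.30 = 300; 1000 × 76/221 = 344. The stated 300-350 is a fair rounding of these two.
- Expected events: 300 × 0.031 = 9.3 and 350 × 0.031 = 10.85; 300 × 0.084 = 25.2 and 350 × 0.084 = 29.4. These match the stated 9.3-10.9 and 25.2-29.4.
- 95% ranges at n = 300, p ± 1.96 × √(p(1−p)/n): 3.1% ± 1.96 points = 1.1%-5.1%; 8.4% ± 3.14 points = 5.3%-11.5%. Both match.

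**Step 2: chance of reaching 300 at the planning share.** Let X be the number with moderate renal impairment among 1000, X ~ Binomial(1000, p), and P(X ≥ 300) = 1 − P(X ≤ 299).
- At p = 0.30: mean 300, SD √(1000 × 0.30 × 0.70) = 14.5.
- Exact P(X ≥ 300) = 0.512; 2.5% and 97.5% quantiles 272 and 329.

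**Step 3: sensitivity to the share.**

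| Share | P(X ≥ 300 of 1000) |
|---|---|
| 28% | 0.085 |
| 29% | 0.253 |
| 30% | 0.512 |
| 31% | 0.763 |
| 32% | 0.918 |
| 33% | 0.981 |
| 34.4% | 0.999 |

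With 1000 patients, a share of about 32.4% is needed for a 95% chance of at least 300. At a 30% share, the total would have to be about 1081 for the same assurance. The domestic share is itself uncertain: 0.344 ± 1.96 × √(0.344 × 0.656/221) gives about 28% to 41%, so it does not rule out shares at which the minimum would probably be missed.

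**Step 4: effect on precision at 272, the lower end of the range at 30%.**
- 3.1%: half-width 1.96 × √(0.031 × 0.969/272) = 2.06 points, range 1.0%-5.2%. The loss against n = 300 is 2.06 − 1.96 = 0.10 points.
- 8.4%: half-width 1.96 × √(0.084 × 0.916/272) = 3.30 points, range 5.1%-11.7%. The loss is 3.30 − 3.14 = 0.16 points.

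**Step 5: what is being counted.** Table 5 in 7.5.2 labels moderate renal impairment as eGFR below 50 mL/min/1.73m², and its foreign-study column includes two patients below 30. The corresponding SAP 5.4 subgroup is eCLCr 30 to below 50 mL/min by the Cockcroft-Gault formula (SAP 8.2.2). Section 7.5.1 does not say which definition the 300 refers to, and the share may differ between them.

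**The case against.** The strongest reply is that the minimum in 7.5.1 is a recruitment requirement. That section is the only place where the planned size is set, so the target number in 7.2.4 and 7.2.5 could include the 300, with registration running past 1000 if needed. Sex, age, weight and serum creatinine are on the Registration Form (7.3.1), so the subgroup could be counted at entry. This reading is possible but not written. Section 7.5.2 twice calls 1000 the target sample size, so the more natural reading is that registration stops at 1000, and it has an end date in any case.

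The second reply is that 0.51 belongs to one exact value of a share given only as approximate. This stands. The 30% is the low end of the 30%-35% implied by 300-350, and at 34.4% the minimum is met almost surely. A share slightly below 30% lowers the chance just as quickly. The honest statement is therefore a range of probabilities.

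The third reply is that nothing formal depends on 300. SAP 4.1 treats all tests as exploratory and SAP 4.2 has no decision rules. This also stands and limits the weight of the point.

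A reader might go further and infer that the sample-size arithmetic is wrong, that 300-350 contradicts the 30%, or that the subgroup will probably fall short. The documents support none of these. Every stated figure reproduces, 300-350 follows from the two shares the plan weighed, and the true share in the enrolled population is not known from the documents.

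**Conclusion.** The stated minimum of 300 is not secured by the design as written. Section 7.5.2 supports 300 as an expectation, and at exactly a 30% share the chance of reaching it among 1000 is 0.51 (95% range of the count 272 to 329). This assumes a total of 1000, independent patients with a common share, and no subgroup quota. Over shares of 29% to 34.4% the chance runs from 0.25 to 0.999.

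The consequence is small. Even at 272 patients the half-widths grow by only 0.10 and 0.16 points, and no hypothesis or decision rule changes. It is worth correcting because it concerns the stated size of the primary-objective population.

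**What to change.** In 7.5.1 and 7.5.2, replace the minimum with an expectation: *about 300-350 expected; 95% range 272-329 at a 30% share*. Give the subgroup precision at 272 (1.0%-5.2% and 5.1%-11.7%) beside that at 300 (1.1%-5.1% and 5.3%-11.5%). Once registration is closed, give it at the achieved count instead. State which definition of moderate renal impairment the count uses, eGFR as in Table 5 or eCLCr as in SAP 5.4.

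A new closing rule in 7.2.4 would not help this study on its own schedule: planned registration ended in June 2018, before the amended protocol of 1 December 2018, and the SAP revision history records observation as completed by July 2020. The study report should therefore give the achieved count and the precision it supports, and should not describe 300 as guaranteed by design.

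The cost is a few sentences and slightly less favourable stated precision. No new data collection or analysis is needed.

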7.5.2. Rationale for sample size

Table 5 shows the number and proportion of cases of adverse events related to hyperkalaemia and renal impairment that occurred within 52 weeks (364 days) after the start of administration, for which a causal relationship could not be ruled out, in all CHF patients and patients with moderate renal impairment in the domestic Phase III study (Study A6141114) and the foreign Phase III study (Study EMPHASIS-HF).

Table 5. Adverse Events related to Hyperkalaemia and Renal Impairment that Occurred within 52 Weeks (364 Days) after the Start of Administration in Eplerenone Group for which Causal Relationship Could Not Be Ruled Out - Safety Analysis Set

Patients with moderate renal impairment eGFR < 50 mL/min/1.73m ²	All CHF patients
N=37	N=111
2 (5.4)	3 (2.7)
0	1 (0.9)
1 (2.7)	1 (0.9)
N=224 a	N=1360
20 (8.9)	56 (4.1)
1 (0.4)	4 (0.3)
6 (2.7)	12 (0.9)
	impairment eGFR < 50 mL/min/1.73m ² N=37 2 (5.4) 0 1 (2.7) N=224 a 20 (8.9) 1 (0.4)

n (%)

In Study A6141114, the ratio of patients with moderate renal impairment to all CHF patients in Japanese was 34.4% (76/221). Taking into account this result and the results of a Japanese epidemiological survey³), the ratio of patients with moderate renal impairment to CHF patients in Japan is estimated to be approximately 30%. Given that the target sample size of all CHF patients is 1000 patients, the number of patients with moderate renal impairment is expected to be approximately 300-350.

As shown in Table 5, the incidence rate of adverse events related to renal impairment for which a causal relationship could not be ruled out was 3.1% (8/261) in patients with moderate renal impairment in the combined results from Study A6141114 and Study EMPHASIS-HF conducted in CHF patients with systolic dysfunction in which the same primary endpoint (cardiovascular deaths or hospitalization due to heart failure) was compared to a placebo treatment group. Assuming that 3.1% is the true incidence rate of adverse events related to renal impairment for which a causal relationship cannot be ruled out in patients with moderate renal impairment, the expected number of cases of adverse events related to

^a: Including two patients with eGFR <30 mL/min/1.73m².

renal impairment for which a causal relationship cannot be ruled out is 9.3-10.9 when collecting 300-350 patients with moderate renal impairment.

Also, assuming that 8.4% (22/261) is the true incidence rate of adverse events related to hyperkalaemia for which a causal relationship cannot be ruled out in patients with moderate renal impairment, similarly to the above-mentioned method, the expected number of cases of adverse events related to hyperkalaemia for which a causal relationship cannot be ruled out is 25.2-29.4.

If events which true incidence rate is 3.1% and 8.4% are observed in 300 patients, the estimated incidence rate will be 1.1%-5.1% and 5.3%-11.5%, respectively, with a probability of approximately 95%.

Assuming that the true incidence rate of adverse events related to renal impairment and hyperkalaemia in all CHF patients for which a causal relationship cannot be ruled out is 1.2% (18/1471) and 4.0% (59/1471), respectively, the expected number of cases of adverse events for which a causal relationship cannot be ruled out is 12.0 and 40.0, respectively, when collecting 1000 CHF patients. Events can be observed in approximately 6-19 patients and 28-53 patients, respectively, with a probability of approximately 95%.

If events which true incidence rate is 1.2% and 4.0% are observed in 1000 patients, the estimated incidence rate will be 0.5%-1.9% and 2.8%-5.2%, respectively, with a probability of approximately 95%.

As described above, regarding adverse events related to hyperkalaemia and renal impairment for which a causal relationship cannot be ruled out, a target sample size of 1000 patients may enable evaluation of the safety profile between clinical studies and use-results surveys in terms of patient background including the presence/absence of comorbid moderate renal impairment as well as seriousness, outcome, etc. of adverse events.

